### 14.3 Relationship to Trial Drug Assessment Definitions

Definitely: Temporal relationship to the administration of the study drug and course following a known reaction pattern;

Probably: Good reasons and sufficient documentation to assume a causal relationship;

Possibly: A causal relationship is conceivable and cannot be dismissed;

Unlikely: The event is most likely related to an etiology other than the trial treatment;

Not Related: No temporal relationship to the administration of the drug or other factors have caused the event;

For reporting purposes, the categories "Definitely", "Probably" and "Possibly" will be summarized as "Suspected" Adverse Reactions. AEs with missing causality assessment will be regarded as possibly related unless further specified.

The sponsor will classify all related SAEs as either expected or unexpected:

Expected: an AE that is listed in the current Investigator's Brochure of MV-CHIK

Unexpected: an AE that is not listed in the current Investigator's Brochure, or it differs because of greater severity or greater specificity

All SAEs that are considered unexpected and suspected to be related to the IMP qualify for a SUSAR (Suspected Unexpected Serious Adverse Reaction) and require expedited reporting.

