All subjects of the measles booster group M1 and M2 will receive five i.m. injections on study day -28, 0, 28, 168 and 196. The first vaccination will be Priorix® (or equivalent measles vaccine) on study day -28. Group M1 will receive MV-CHIK high dose vaccinations on day 0 and day 28 and placebo on day 168 and 196. Group M2 will receive placebo on day 0 and 28 and MV-CHIK high dose on day 168 and on day 196.

All subjects will be followed for safety and immunogenicity evaluation until day 224.

The estimated study duration per subject will be 33-37 weeks (~8 months), respectively. Overall study duration estimates to be 3 years from study initiation until reporting.

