### **8.2.2 Study day 0 / Visit 1**

Subjects of the treatment groups A-D have performed these Visit 1 procedures together with Visit 0 on one day.

Subjects of group M1 and M2 will return to the site for this outpatient visit 28 ( $\pm$ 5 days) days after Visit 0. The inclusion/exclusion criteria and concomitant medication will be checked again. A symptom-directed physical exam, system-based assessment (only if necessary according to symptom-directed physical exam), assessment of arthralgia and evaluation of vital signs as well as body temperature will be recorded. Blood samples for immunogenicity 1 and measles antibody titer serum sample will be obtained and all study sites except the two sites in Vienna will collect serum samples for cross neutralization and passive transfer analyses (immunogenicity 2). From all subjects enrolled in Vienna blood samples will be

collected for T cell assays. A urine pregnancy test will be performed in women of childbearing potential. Subject diaries of group M1 and M2 will be collected and checked for completeness. Subjects of treatment group M1 and M2 will be assessed for local tolerability of the first vaccination and will then receive their 2nd injection. They will be observed for 1 hour after vaccination before discharge from study site. One hour after vaccination local tolerability and adverse events will be recorded, if applicable.

Subjects will be discharged after dispensing and explanation of the subject diaries, only if the investigating physician considers it to be safe for the subjects to leave the department and are asked to return to study site after 28 days ( $\pm$  5 days).

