**Table 7 Vaccination time points**

Group	Visit 0 day -28	Visit 1 day 0	Visit 2 day 28	Visit 3 day 56	Visit 4 day 168	Visit 5 day 196	Visit 6 day 224	Visit 7 day 286
A, C	V/C		V/C			P		
B, D	P		V/C			V/C		
M1	C	V	V		P	P		
M2	C	P	P		V	V		

V = MV-CHIK vaccine (high or low dose), C = control-vaccine, P = placebo

The investigational medicinal products (IMPs) are described in detail in section 5.1, dosage and sequence ad 1.2, 1.3, 6.1 and Table 1, route of administration in section 5.3 and treatment period in section 8.4

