**Entire study stopping rules**

The study will be stopped (no new enrollments and no additional vaccine administered) pending a full DSMB safety review if any of the following occurs:

- a. One or more subjects experience a suspected adverse reaction (SAR) that is both serious and unexpected, based on the reference safety information (Investigator's Brochure).
- b. One or more subject's death assessed by the investigator, medical monitor or sponsor as related to investigational product.
- c. One or more subjects develop laryngospasm, bronchospasm or anaphylaxis within 24 hours of vaccine administration.
- d. One or more subjects develop injection-site ulceration, abscess or necrosis.
- e. Two or more subjects experience generalized urticaria within 72 hours after administration of study product.

Upon completion of this review and receipt of the advice of the DSMB, the sponsor will determine if study entry or study dosing should be discontinued (or if a dose level should be dropped) or if study entry and study dosing may continue according to the protocol. The competent authorities and ethical committees will be informed whenever the study is stopped for DSMB review.

In case the entire clinical study has to discontinue prematurely or a dose level has to be dropped for any reason, the concerned subjects should be asked to perform an early termination visit. Additionally, women of childbearing potential will be followed up by a phone call, 3 months after the last vaccination to ensure no pregnancy occurred within this period as confirmed by a urine pregnancy test provided by the investigator.

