## 14.5 Collection, Recording and Reporting of Adverse Events

All events meeting the definition of an Adverse Event must be collected and reported starting with randomization (Visit 0/ day -28) until the end of the protocol required post-treatment follow-up period (Visit 6 28 days after the last vaccination).

At each contact to the site (visit or telephone, excluding safety visits) where the subject is not seeing the investigator or his staff (e.g. visits to the laboratory), the subject must be asked about adverse events. All adverse events either observed by the investigator or reported by the subject must be recorded by the investigator and evaluated.

The subjects will be asked in general: "How are you?" as well as specifically: "Have you experienced any problems since the last contact?"

The investigator should record the diagnosis, if available. If no diagnosis is available, the investigator should record each sign and symptom as individual adverse events.

The investigator must record all adverse events in the eCRF. One single adverse event line must be used per adverse event, from start to resolution. For serious adverse events, the Serious Adverse Event Report Form must also be completed.

The investigator must report all SAEs with the completed SAE Report Form within 24 hours after learning of its occurrence to:

Assign Safety Desk: [contact]

Email: [[contact]](mailto:[contact])

For urgent questions please call the 24-hours Safety [contact]**

Under certain circumstances the first notification can be done by phone; nevertheless, a written Serious Adverse Event Report Form has to be submitted for confirmation to Assign Safety Desk. Reporting timelines are applicable also if the SAE is not felt to be treatment-related. The monitor must be informed accordingly.

The original copy of the SAE Report Form and the fax confirmation sheet must be kept with the documentation at the study site.

Please note: Each SAE has also to be documented in the eCRF as a serious adverse event in the corresponding AE section.

The sponsor is responsible to fulfill the requirements of expedited reporting of all SUSARs (Suspected Unexpected Serious Adverse Reaction) to the Competent Authorities, Ethics Committees and principal investigators concerned according to national and European law and regulations.

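### Protocol 14.3 and whole-study stopping rule 11.3(a) judge expectedness only against the MV-CHIK brochure, although M1/M2 subjects have received only an MMR vaccine between day -28 and day 0

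*Protocol*

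**What the plan says.** Protocol 14.3 states that "The sponsor will classify all related SAEs as either expected or unexpected". The test is: "Expected: an AE that is listed in the current Investigator's Brochure of MV-CHIK". An event is unexpected if it is missing from that brochure, or is more severe or more specific than its entry there. A related SAE classed as unexpected is a SUSAR and needs expedited reporting.

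Protocol 11.3, under the rules for the entire study, halts enrolment and vaccination pending a full DSMB review if "One or more subjects experience a suspected adverse reaction (SAR) that is both serious and unexpected, based on the reference safety information". The text then names the Investigator's Brochure as that reference. (A separate item (a) in 11.3 concerns individual subjects and is not at issue.)

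For M1 and M2, section 6.1 says: "The first vaccination will be Priorix® (or equivalent measles vaccine) on study day -28". The next injection is at Visit 1 on day 0, of which section 8.2.2 says: "Subjects of group M1 and M2 will return to the site for this outpatient visit", 28 days (±5) after Visit 0. Section 6.4 states that membership of M1/M2 is open; only the order of injections is blinded. Under section 14.5, adverse events are collected from day -28.

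**The concern.** Expectedness should be judged against the safety information of the product under suspicion. Here a single brochure, written for MV-CHIK, serves every related SAE, including those that can be suspected only of an MMR vaccine.

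Two actions depend on the answer: expedited reporting as a SUSAR, and rule (a), under which one event stops enrolment and dosing in every group until the DSMB has reported. The wrong reference could distort either action in either direction:

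- A reaction listed for MMR but absent from the brochure would be unexpected. It would become a needless SUSAR and pause the whole study.
- A reaction in the brochure but not listed for MMR would be expected. Section 14.3 would not make it a SUSAR, and rule (a) would not apply.

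**Working it through.** **1. Is the MMR vaccine inside the rule?** The note under Table 7 (section 9.1.1), whose key lists MV-CHIK, control vaccine and placebo, says: "The investigational medicinal products (IMPs) are described in detail in section 5.1". Section 5.1 covers MV-CHIK (5.1.1) and the control treatments (5.1.2). In section 5.5 the label for the ready-to-use IMP syringe also names Priorix. So the control vaccine is handled as an IMP, and 14.3 covers all related SAEs without a split by product.

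**2. Does another section supply a reference for MMR?** No. The brochure in section 16.1 is for the investigational product, in the singular. A package insert is mentioned in section 19.2, but only among the papers submitted to the ethics committee. No section uses it to judge expectedness.

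**3. Which study product can be suspected between day -28 and day 0?** Under section 6.1, M1 receives MV-CHIK first on day 0 and M2 first on day 168. Before the day 0 injection both groups have had only MMR. Because membership is open, this is known without breaking the blind.

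**4. Could the two reference lists differ?** By section 5.1.1, MV-CHIK is the Schwarz measles strain with Chikungunya sequences inserted. By section 5.1.2, Priorix shares the Schwarz strain but adds mumps and rubella viruses. MMR-Vax-Pro, the permitted substitute, has a different measles strain plus mumps and rubella, and contains hydrolysed gelatin. The lists may therefore overlap on measles-type reactions and differ elsewhere. Neither list is among the documents.

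**5. How many subjects?** Inputs are from Table 1 and section 6.3.

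- Total: 4×60 + 4×10 + 20 + 20 = 320, which reproduces the stated 320.
- Open MMR-only window: 20 + 20 = 40 subjects.
- Length of the window: 40×28 = 1,120 subject-days. With the ±5-day visit window it runs from 40×23 = 920 to 40×33 = 1,320.
- For context, any MMR exposure: 40 controls in A–D + 40 in M1/M2 = 80 of 320 (25%).
- MMR doses: 40×2 + 40×1 = 120. MV-CHIK doses: 240×2 + 40×2 = 560. MMR share: 120/680 = 17.6%.

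**6. How likely is an event in the window?** The documents give no rate. Let p be an assumed chance, per day -28 dose, of an SAE judged related. The chance of at least one among 40 doses is 1 − (1 − p)^40:

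| Assumed p | At least one in 40 |
|---|---|
| 0.001% | 0.04% |
| 0.01% | 0.4% |
| 0.1% | 3.9% |

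These figures are illustrations. Each must still be multiplied by the unknown chance that the two lists treat that event differently, so none of them estimates a misclassification.

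**The case against.** The strongest reply is that no consequence is shown. The rule does harm only if the two lists differ on a serious reaction. Neither list can be seen, and the shared Schwarz strain makes overlap plausible. That stands: the text shows a wrong reference, not a wrong classification.

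The second reply is that other provisions catch the problem. The DSMB reviews any SAE within a week of its report and sees unblinded data (11.1). SUSARs must go to the authorities, ethics committees and principal investigators "concerned according to national and European law and regulations" (14.5). Ethics committees also receive new adverse safety information (19.2), and authorities receive SAE reports (19.3). The treatment-group rules and whole-study rules (b) to (e) do not depend on expectedness, and rule (a) stops the study only until the DSMB has reviewed it. All this limits the harm. It does not repair rule (a): the sponsor, not the DSMB, makes the 14.3 classification, and a listed MMR reaction missing from the brochure would stop the study before that review.

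One could also read IMP in 14.3 as MV-CHIK alone. An SAE suspected of MMR would then have no SUSAR rule, while 14.3 still classifies all related SAEs. That reading needs clearer wording too.

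For blinded events the opposing case is good. A single reference avoids unblinding individual cases. Choosing the reference by product received would require opening dosing records that section 5.8 restricts to an unblinded monitor. A rule that treats an event as unexpected if it is unlisted for either suspected product would also change how often rule (a) fires. These are trade-offs, not corrections.

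Finally, the SAP rests on separate Austrian and German protocols. The supplied protocol matches the SAP's German schedule (Visit 7, high-dose M1/M2), although it lists Austrian sites. Whether the Austrian 14.3 reads the same cannot be checked, so the count of 40 assumes that it does. The SAP's low dose for Austrian M1/M2 does not matter here, because those subjects also start with MMR.

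**Conclusion.** The point holds for the open window and is minor. For 40 planned M1/M2 subjects between the day -28 and day 0 injections, the stated rule applies the wrong product's reference. It rests on the protocol's own treatment of MMR as an IMP and on the absence of any other reference for expectedness.

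A reader might infer three stronger things that the documents do not support:

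- That a related SAE in the window must be a true MMR reaction. Section 14.3 counts possible relationships as suspected reactions and treats a missing causality assessment as possibly related. The supported statement is that MMR is the only study product that can be suspected.
- That events will be misclassified, or at a known rate. The lists are unseen and the rates above are assumed.
- That the same clear error extends to the A–D controls, or to M2 up to day 168. Those subjects have had no MV-CHIK either, but this is not known without unblinding.

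No endpoint, analysis population or SAP analysis uses expectedness, so the trial's statistical results are unaffected.

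**What to change.** In 14.3 and in entire-study rule (a) of 11.3, define the reference safety information by product: the MV-CHIK brochure for MV-CHIK, and the current product information of the control vaccine actually used for MMR. State that the latter applies to M1/M2 events before the day 0 injection.

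This costs a few lines of wording. The package insert of a marketed product is already on the submission list in 19.2. No unblinding is needed, and the stopping thresholds stay as they are.

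For blinded events (A–D, and M1/M2 from day 0), the choice of reference can be left to the sponsor's existing safety procedures. A dedicated unblinded function, or a rule for events unlisted for either suspected product, is optional. The first would need wider access to dosing records and unblinding of single cases, and the second would change how often rule (a) fires.

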### 14.4 Outcome Categories and Definitions

#### Recovered

Stabilized: An AE is stabilized when, according to the investigator, the subject is in a clinically stable condition. This term should only be used for chronic conditions and for a given subject only when he/she has completed the protocol.

Recovered with sequelae: As a result of the SAE, the subject is suffering from persistent or significant disability/incapacity (e.g. became blind, deaf, paralyzed). Any AE recovered with sequelae should be rated as an SAE since an SAE criterion is fulfilled.

#### Not Recovered

Ongoing at final examination

Died

## 14.5 Collection, Recording and Reporting of Adverse Events

All events meeting the definition of an Adverse Event must be collected and reported starting with randomization (Visit 0/ day -28) until the end of the protocol required post-treatment follow-up period (Visit 6 28 days after the last vaccination).

At each contact to the site (visit or telephone, excluding safety visits) where the subject is not seeing the investigator or his staff (e.g. visits to the laboratory), the subject must be asked about adverse events. All adverse events either observed by the investigator or reported by the subject must be recorded by the investigator and evaluated.

The subjects will be asked in general: "How are you?" as well as specifically: "Have you experienced any problems since the last contact?"

The investigator should record the diagnosis, if available. If no diagnosis is available, the investigator should record each sign and symptom as individual adverse events.

The investigator must record all adverse events in the eCRF. One single adverse event line must be used per adverse event, from start to resolution. For serious adverse events, the Serious Adverse Event Report Form must also be completed.

The investigator must report all SAEs with the completed SAE Report Form within 24 hours after learning of its occurrence to:

Assign Safety Desk: [contact]

Email: [[contact]](mailto:[contact])

For urgent questions please call the 24-hours Safety [contact]**

Under certain circumstances the first notification can be done by phone; nevertheless, a written Serious Adverse Event Report Form has to be submitted for confirmation to Assign Safety Desk. Reporting timelines are applicable also if the SAE is not felt to be treatment-related. The monitor must be informed accordingly.

The original copy of the SAE Report Form and the fax confirmation sheet must be kept with the documentation at the study site.

Please note: Each SAE has also to be documented in the eCRF as a serious adverse event in the corresponding AE section.

The sponsor is responsible to fulfill the requirements of expedited reporting of all SUSARs (Suspected Unexpected Serious Adverse Reaction) to the Competent Authorities, Ethics Committees and principal investigators concerned according to national and European law and regulations.

## 14.6 Follow-up of Adverse Events

During and following a subject's participation in a clinical trial, the investigator/institution will ensure that adequate medical care is provided to the subject for any adverse events, including clinically significant laboratory values related to the trial. The investigator/institution will inform the subject when medical care is needed for adverse event(s) of which the investigator becomes aware. All non-serious adverse events classified as severe or definitely/possibly/probably related to the trial product must be followed until 28 days after the administration of MV-CHIK or control (vaccine or placebo). All serious adverse events must be followed until the subject has recovered, stabilized, recovered with sequelae or died.

All other adverse events must be followed until the subject has recovered or stabilized or until the end of the protocol required post-treatment follow-up whichever comes first, and until all adverse event related queries for the subject have been resolved.

Follow-up information about a previously reported SAE must also be reported within 24 hours of the investigator receiving it. The initial SAE report form should be used, stating that this is a follow-up report to the previously reported SAE and giving the date of the follow-up report. The information provided should describe whether the event has resolved or continues, if and how it was treated, and whether the subject continued or discontinued study participation, if not already stated in the initial report.

The original copy of the SAE form including any follow-up information and the fax confirmation sheet must be kept with the documentation at the study site.

## 14.7 Reporting of Pregnancies

Women must not become pregnant during the entire clinical study period and 6 months after the last vaccination. If a subject becomes pregnant within this period, she must immediately inform the investigator of the pregnancy. The investigator will complete a corresponding Pregnancy Report Form and send the form within 24 hours after becoming aware to Assign Safety Desk via fax. The first notification can be done via phone (24-hours safety [contact]), nevertheless a written Pregnancy Report Form must be submitted for confirmation. If the pregnancy occurs during the study the subject should attend follow-up visits as planned. In addition, subjects who become pregnant during the study (and who received at least one dose) or subjects who become pregnant within 6 months after the last vaccination

(even in case of withdrawal or early termination for any reason) will be followed until pregnancy outcome, even if this occurs after the study is completed.

## **15 QUALITY CONTROL AND QUALITY ASSURANCE**

### **15.1 Source Data and Records**

Source data are defined as all information related to clinical findings, observations, or other activities in the study, written down in original records or certified copies of original records. The investigator will permit study-related monitoring, audits, IRB/IEC review and regulatory inspections, by providing direct access to source data/records. Source records should be preserved for the maximum period of time required by local regulations.

At least the following data will be documented in the source records:

- Date of subject's study entry and termination, study identification
- Documentation of informed consent procedure
- Date of each study visit and study related correspondence
- Medical history, demographic data
- Any examination findings, including local injection site reactions
- Adverse events
- Concomitant medication intake
- Early withdrawal date and withdrawal reason, if applicable
- Dosing dates
- Subject number
- Completed subject diaries

Source data entries must be made in accordance with local requirements. Signed and dated copies of the laboratory result reports have to be kept within the subject's files.

